Statistical tables will be generated using SAS version 9.4 or higher. Disposition of all randomized subjects will be summarized by treatment and listed for each subject. Demographic and baseline characteristics will be listed and summarized for the safety population using descriptive statistics. Each subject's exposure to study drug will be listed. Adverse events will be coded using a standardized Medical Dictionary for Regulatory Activities (MedDRA), Version 23.0 or higher. Prior and concomitant medications will be coded using the World Health Organization (WHO) Drug Enhanced Dictionary (March 2020 or later). Tabulations will be prepared including all AEs and all AEs by relationship and severity using Common Terminology Criteria for Adverse Events Version 5.0 [CTCAE v5]. Adverse events resulting in early termination and events meeting regulatory criteria for seriousness will also be tabulated separately. By subject listings of all safety data and concomitant medication use will be generated.

This study will be conducted in accordance with the guidelines of Good Clinical Practices (GCPs) including archiving of essential documents.

Table 1: Schedule of Procedures

	Screen	Subjects Resident in Clinical Research Unit												FU Tel Call				
		Day	-28 to -1	-1	Day 1								2	3*	Day 8 ± 2			
Hour					0	0.25	0.5	0.75	1	1.5	2	4	6	9	12	24	36	48
Informed Consent	X																	
Eligibility Assessment	X	X																
Demographics	X																	
Admission to CRU																		
Randomization																		
Medical History																		
Physical Exam ¹																		
Height, Weight, BMI																		
Weight																		
Resting 12-lead ECG ²																		
Vital signs (BP, PR, RR, Oral Temp)																		
Clinical laboratory tests ³																		
HIV, Hep B&C screen																		
Drug/alcohol screen																		
Pregnancy test ⁴																		
FSH and estradiol ⁵																		
Dose administration ⁶																		
PK blood samples																		
Injection site assessment																		
AE & ConMeds																		
Discharge from CRU																		

NOTE: all timed procedures are with respect to START of study drug infusion.

AE= adverse event; BP = blood pressure; con med = concomitant medications; CRU = clinical research unit; ECG = electrocardiogram; FU = Follow-up; HIV = human immunodeficiency virus; Hep = Hepatitis; PR = pulse rate; PK = pharmacokinetics; RR = respiratory rate.

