*Day 3 is the completion visit. Assessments to be performed on Day 3 prior to discharge from the CRU or at early termination; physical exam, vital sign assessments, clinical laboratory tests and ECG.

¹A full physical exam will be conducted at screening and an abbreviated physical exam will be conducted on Day -1 and Day 3.

²Pre-dose and 1.5 h post infusion start ECGs will be triplicate ECGs (Triplicate ECGs will be performed approximately 1 minute apart).

³Clinical laboratory samples include: hematology, chemistry, coagulation parameters PT/INR/aPTT, and urinalysis.

⁴For female subjects – Serum pregnancy test at screening and urine pregnancy test at admission, both must be negative to enroll in the study.

⁵FSH and estradiol levels will be assessed in postmenopausal females to confirm status.

⁶IV infusion will occur at approximately 8:00 am, following completion of a low-fat breakfast. Infusion will over an approximately 60 minute period. Infusion stop time will have a time window of ± 5 minutes.

Time windows: Vital signs and ECGs: Pre-dose: within 60 min prior dosing; post-dose to ≤ 12 h: (± 15 min); ≥ 24 h: (± 30 min).

PK sampling: pre-dose (-60 min), < 2 h (± 5 min), 2 to < 24 h (± 10 min), 24, 36 and 48 h (± 15 min).

Injection site assessments: pre-dose (-60 min), ≤ 24 h (± 30 min).

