10.3 Treatment Compliance

Intravenous dose administration will be conducted and monitored by CRU personnel. Subjects will be encouraged to use the restroom prior to the start of infusion. The date and time of start and stop of infusion will be recorded on the eCRF. If an infusion needs to be interrupted, the time of infusion interruption (stop and restart time) will be recorded.

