11.3 Study Drug Preparation and Dosing

The clinical site pharmacist or designee will prepare the study drug according to the randomization scheme, maintain the drug packaging and labeling log, and keep the blinding for treatment assignment per the randomization scheme. Study drug will be administered to subjects by CRU staff at approximately 8:00 a.m., following completion of a low-fat breakfast.

HF1K16 for Injection doses will be calculated based on subject weight measured at admission, and diluted in sterile saline (0.9% sodium chloride) according to [Table 4](#). All calculations will be documented in the pharmacy log. The preferred injection site for IV infusion is the antecubital region of the upper extremity. Doses will be administered using an IV infusion pump over a period of approximately 60 minutes at 2.5 mL/min, with details to be provided in a separate manual. Dose date and time, including any unscheduled stop times, and site of injection will be documented in the eCRF.

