### **5 Pharmacokinetic Analysis**

Plasma samples for the PK analysis of HF1K16 (free tretinoin and liposome encapsulated tretinoin) will be collected relative to Day 1 dosing.

Blood samples for plasma tretinoin and 4-oxotretinoin PK analysis will be collected within 60 minutes prior to start of infusion, and 0.5, 1, 1.5, 2, 4, 6, 9, 12, 24, 36, and 48 hours relative to start of infusion.

A deviation within allowable time windows will not be considered as a protocol deviation as long as the actual sampling time is recorded, refer to the following [Table 3](#) for allowed time window deviations.

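### No PK sample is tied to the actual end of infusion, so if concentration peaks there, observed Cmax can miss the peak by a few percent on average; the remedy needs no extra sample

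*Protocol*

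**What the plan says.** Protocol Table 1 carries the note "NOTE: all timed procedures are with respect to START of study drug infusion". SAP Section 5 lists the post-dose PK times as "0.5, 1, 1.5, 2, 4, 6, 9, 12, 24, 36, and 48 hours relative to start of infusion". None is defined by the end of infusion.

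The infusion runs "over a period of approximately 60 minutes at 2.5 mL/min" (Protocol Section 11.3), and the Table 1 footnote adds: "Infusion stop time will have a time window of" ± 5 minutes. The early samples have the same tolerance: "PK sampling: pre-dose (-60 min), < 2 h (± 5 min"; Protocol Section 12 and SAP Table 3 repeat it.

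Protocol Section 10.3 states: "The date and time of start and stop of infusion will be recorded on the eCRF". It also provides for recording interruptions. Protocol Section 12.5 and SAP Section 5.2 call for non-compartmental analysis with actual times. The SAP glossary defines Cmax as an observed maximum. Cmax is among the primary PK parameters (Protocol Section 12.5) and is a response in the dose-proportionality model (Protocol Section 14.3, SAP Section 5.3).

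**The concern.** With a constant-rate infusion of drug that is measured directly in plasma, concentration rises until the pump stops and then falls. The end of infusion is therefore the moment to sample for Cmax. Here the nominal stop and the nominal 1-h draw coincide, but each may move independently by 5 minutes. If both windows are used evenly, about half of subjects are sampled while the pump is still running and half after it has stopped.

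Using actual times puts Tmax and the AUC time axis right. It cannot help Cmax, because a non-compartmental Cmax is the largest value measured. At stake is the accuracy of one primary PK parameter in the first human study of the intravenous product, with six active subjects per cohort. The matter is most relevant where elimination is fast, and Protocol Section 5.1 describes the half-life of circulating ATRA as very short without giving a figure.

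**Working it through.** The documents give no half-life, assay precision or target precision for Cmax, so there is no planned figure to reproduce.

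**Inputs from the documents.** Infusion stop T = 60 ± 5 min; samples at 30, 60 and 90 min, each ± 5 min, all from infusion start.

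**Assumptions.** One compartment; a fixed dose given at a constant rate over T; half-life from 0.25 to 24 h, with short values standing for free tretinoin and long values for encapsulated drug; stop and draw times independent and uniform over their windows.

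**Formulas.** With k = ln 2 / half-life, a sample at time t relative to the true peak C(T) is
- t ≤ T: (1 − e^(−kt)) / (1 − e^(−kT))
- t > T: e^(−k(t − T))

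Observed Cmax is the largest of the 0.5-h, 1-h and 1.5-h samples.

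**Extreme cases.**
- Half-life 0.5 h (k = 1.386 per h), stop 55 min, draw 65 min: e^(−1.386 × 10/60) = 0.794, a loss of 20.6%.
- Half-life 1 h (k = 0.693), same times: e^(−0.693 × 10/60) = 0.891, a loss of 10.9%.
- Half-life 2 h (k = 0.3466), stop 65 min, draw 55 min: (1 − 0.7278)/(1 − 0.6870) = 0.870, a loss of about 13%. The 1.5-h sample at its nominal 90 min gives e^(−0.3466 × 25/60) = 0.866, so it does not help.
- Half-life 24 h (k = 0.0289), stop 65 min, draw 55 min: the 1-h sample alone is 15.2% low, but a 1.5-h sample at 95 min gives e^(−0.0289 × 30/60) = 0.986, so the loss is only 1.4%.

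**Average over uniform windows (simulation).** The last column draws the 1-h sample within ± 2 min of the actual stop.

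| Assumed half-life | Mean loss, current plan | Mean loss, anchored ± 2 min |
|---|---|---|
| 0.5 h | 4.9% | 1.5% |
| 1 h | 3.7% | 1.2% |
| 2 h | 3.2% | 1.0% |
| 24 h | 0.7% | 0.6% |

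Under the current plan the mean loss is 6.4% at 0.25 h, 2.6% at 4 h and 1.7% at 8 h. At 0.5 h about 15% of subjects lose more than 10%. If timing errors are instead normal with SD 2 min, clipped at 5 min, the mean loss is 2.8% at 0.75 h and 1.9% at 4 h. With stop and draw both exactly at 60 min it is zero.

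**Assay error added** (assumed CV 10%, samples to 6 h included). Net mean bias is −4.1% at 0.75 h, −1.9% at 2 h, +3.6% at 8 h and +7.2% at 24 h, because the maximum of several noisy, similar values is biased upward.

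**Power-model slope** (doses 3, 6, 10, 13 mg/m²; six subjects each; between-subject SD 0.3 on the log scale, assumed). The mean slope is 1.000 with or without timing error. Its SD moves from 0.110 to 0.111 at 0.75 h and from 0.109 to 0.110 at 4 h.

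**The case against.** The strongest objection is that the peak may not be at the end of infusion for the analyte that matters most. HF1K16 is encapsulated ATRA. If free tretinoin arises mainly by release from liposomes, it peaks after the pump stops. A check with no free drug in the bag, release half-lives of 2 to 8 h and free-drug half-lives of 0.25 to 1 h put the free-drug peak at 1.5 to 4.0 h. The 1-h sample reached only 36% to 81% of that peak, so moving it did not change Cmax. The documents do not settle the release kinetics, so this stands as a condition on the finding. The remark on a very short half-life concerns existing ATRA treatment, and Protocol Section 6.1.2 says that the HF1K16 profile differs.

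The windows are also tolerances rather than expected errors. A pump sets the rate, and Protocol Section 12 asks staff to keep to the specified times. Uniform draws over the full windows are therefore pessimistic. Infusion and blood-collection details are deferred to separate manuals (Protocol Sections 11.3 and 12.1), which may already coordinate the draw with the pump stop.

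A reader might go further and infer that reported Cmax is always too low, that the timing adds material scatter in cohorts of six, that dose proportionality is distorted, or that escalation is affected. The documents do not support these. The downward direction belongs to timing error alone and can be outweighed by assay error. The slope SD barely moves. The same scheme applies at every dose, so the slope is not biased if kinetics do not change with dose. The exposure limit in Protocol Section 10.6 is set on AUC.

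**Conclusion.** The point holds as a low-severity design improvement; the plan contains no contradiction here. No sample is anchored to the actual stop, and the 1-h draw can be up to 10 minutes from it, or more after an interruption. If concentration peaks at the end of infusion, timing error alone costs about 1% to 6% of Cmax on average, and 10% or more in some subjects when the half-life is about 2 h or less. Actual times do not restore this. The size rests on the assumed half-lives, the one-compartment model and uniform windows. For slowly cleared encapsulated drug the 1.5-h sample already limits the loss.

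**What to change.** In the Protocol Table 1 footnote and SAP Section 5 (including its window table), redefine the existing 1-h PK sample as the end-of-infusion sample, drawn within ± 2 minutes of the actual pump stop. Leave the other sampling times unchanged, and align the windows in Protocol Section 12 and the collection manual.

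The narrow two-sided window matters. A draw 0 to 5 min after the stop would lose 5.6% on average at a 0.5 h half-life, more than the present 4.9%. A draw only in the 2 min before the stop does better there (0.8%) but raises the mean loss at 24 h from 0.7% to 1.1%. In the model, ± 2 min is no worse on average than the current plan at any half-life from 0.25 to 24 h.

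The cost is a footnote, matching SAP and manual text, and slightly tighter nursing coordination. No extra sample is needed, and the stop time is already recorded.

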12 PHARMACOKINETIC ASSESSMENTS

Blood sampling time points are listed in [Table 1](#).

Deviations from planned blood sample collection times are acceptable based on logistical and operational considerations as follows:

- 0 h/pre-dose: within 60 minutes prior to dosing
- <2 hours post-dose: \pm 5 minutes
- 2 hours to \leq 24 hours: \pm 10 minutes
- 24, 36 and 48 hours: \pm 15 minutes

Every effort will be made to collect PK samples at the protocol-specified time. Other assessments e.g. ECG, vital signs etc. may be taken before or after PK sample collection.

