13.1 Safety Parameters

13.1.1 *Demographic/Medical History*

Demographic characteristics (age, sex, race, and ethnicity) will be collected at the screening visit. Medical history will be reviewed and collected at the screening visit and updated at admission. The subject may be asked to sign a medical release form allowing contact with the subject's doctor for more information about subject's medical history or in case of an AE.

13.1.2 *Vital Signs*

Vital signs, including blood pressure, pulse rate, respiratory rate and oral temperature will be measured after the subject has rested in the supine position for at least 5 minutes.

Vital signs will be monitored for infusion reactions, and will be taken at screening, pre-dose and 0.25, 0.5, 0.75, 1, 1.5, 2, 6, 24 and 48 hours post-dose relative to the start of infusion

Vital signs may be repeated for clinically significant abnormal vital signs at the discretion of the Investigator.

13.1.3 *Physical Examination, Height, Weight, and Body Mass Index*

A full physical examination includes assessment of general appearance and evaluation of dermatological system, head, eyes, ears/nose/throat, neck, lymph nodes, lungs, heart, abdomen, neurological, skin and musculoskeletal system.

An abbreviated physical examination includes assessment of the heart, lungs, abdomen, skin and the neuromuscular system. A symptom-directed physical examination may be performed at any time. All physical examinations will be performed by qualified personnel.

Physical examinations may be repeated at any time during the study in the interest of subject safety, at the discretion of the Investigator.

At the screening visit, height (centimeters) and weight (kilograms) will be measured and BMI will be calculated. Weight will be measured at admission.

13.1.4 *Electrocardiogram*

A standard resting 12-lead ECG will be performed after the subject has rested in the supine position for at least 5 minutes. Parameters assessed will include ventricular rate (bpm), PR interval (msec), QRS complex and duration (msec), ST Segment, T wave, QT interval (msec) and QTcF interval (msec).

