13.2 Adverse Events

Adverse events will be recorded beginning immediately after the Informed Consent Form (ICF) is signed. Subjects will be instructed to report AEs during the study and staff will query subjects regarding AEs throughout the study. The Investigator (and/or designee) must document all AEs reported by the subject from the time subjects give consent through the follow-up/completion visit. Any subject who is withdrawn from the study due to an AE shall be followed until the event has resolved or stabilized, and the Investigator will document available follow-up information on the subject's source documentation and eCRF.

13.2.1 *Definitions of Adverse Events*

An AE is any unfavorable and unintended sign, symptom, or disease temporally associated with the use of medicinal (investigational) product, whether or not related to the medicinal (investigational) product. An AE is any symptom, sign, illness, or experience that develops or

worsens in severity during the course of the study. Adverse events reported after consent but before the first dose of study drug are still to be documented by the Investigator but will be considered non-treatment-emergent AEs. Adverse events will be considered treatment-emergent if the onset date is after the first dose of study drug. The severity of each AE will be graded by the Investigator using the National Cancer Institute (NCI) CTCAE v5.0 as follows:

- **Grade 1:** Mild; asymptomatic or mild symptoms; clinical or diagnostic observations only; intervention not indicated;
- **Grade 2:** Moderate; minimal, local, or noninvasive intervention indicated; limiting age appropriate instrumental activities of daily living (ADL);
- **Grade 3:** Severe or medically significant but not immediately life-threatening; hospitalization or prolongation of hospitalization indicated; disabling; limiting self-care ADL;
- **Grade 4:** Life-threatening consequences; urgent intervention indicated;
- **Grade 5:** Death related to AE.

Abnormal results of laboratory tests or diagnostic procedures are considered AEs if the abnormality:

- Is associated with clinical signs or symptoms
- Is considered by the Investigator to be of clinical significance
- Results in study withdrawal
- Fulfills any of the criteria for a serious AE (SAE), as described in this section
- Requires treatment

An SAE is any untoward medical occurrence at any dose that:

- Results in death
- Is life threatening

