**NOTE: all timed procedures are with respect to START of study drug infusion.**

AE= adverse event; BP = blood pressure; con med = concomitant medications; CRU = clinical research unit; ECG = electrocardiogram; FU = Follow-up; HIV = human immunodeficiency virus; Hep = Hepatitis; PR = pulse rate; PK = pharmacokinetics; RR = respiratory rate.

\*Day 3 is the completion visit. Assessments to be performed on Day 3 prior to discharge from the CRU or at early termination; physical exam, vital sign assessments, clinical laboratory tests and ECG.

A full physical exam will be conducted at screening and an abbreviated physical exam will be conducted on Day -1 and Day 3.

Pre-dose and 1.5 h post infusion start ECGs will be triplicate ECGs (Triplicate ECGs will be performed approximately 1 minute apart).

Clinical laboratory samples include: hematology, chemistry, coagulation parameters PT/INR/aPTT, and urinalysis.

For female subjects – Serum pregnancy test at screening and urine pregnancy test at admission, both must be negative to enroll in the study.

FSH and estradiol levels will be assessed in postmenopausal females to confirm status.

IV infusion will occur at approximately 8:00 am, following completion of a low-fat breakfast. Infusion will over an approximately 60 minute period. Infusion stop time will have a time window of  $\pm 5$  minutes.

Time windows: Vital signs and ECGs: Pre-dose: within 60 min prior dosing; post-dose to  $\leq 12$  h: ( $\pm 15$  min);  $\geq 24$  h: ( $\pm 30$  min).

PK sampling: pre-dose (-60 min),  $< 2$  h ( $\pm 5$  min), 2 to  $<24$  h ( $\pm 10$  min), 24, 36 and 48 h ( $\pm 15$  min).

Injection site assessments: pre-dose (-60 min),  $\leq 24$  h ( $\pm 30$  min).

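### The ±15 min window on the four vital-sign readings taken during the infusion equals their 15 min spacing, so neighbouring windows overlap by 15 min

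*Protocol*

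**What the plan says.** Protocol section 13.1.2 gives both the purpose and the times: "Vital signs will be monitored for infusion reactions, and will be taken at screening, pre-dose and 0.25, 0.5, 0.75, 1, 1.5" h, then 2, 6, 24 and 48 h, all from the start of infusion. Section 8.1 lists the same times, and SAP Table 2 includes the same four first-hour readings. The synopsis text has a shorter list, which is a separate matter.

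The infusion lasts about 60 minutes. The note under the schedule in both documents counts all times from its start, so the four readings fall during the infusion or at its end.

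The tolerance is in the Table 1 footnotes: "Vital signs and ECGs: Pre-dose: within 60 min prior dosing; post-dose to ≤ 12 h: (± 15 min"). The SAP Table 2 footnotes carry the same line, beginning "Vital signs and ECGs: Pre-dose: within 60 min prior dosing". Neither document gives a narrower vital-sign window for the first hour, a minimum spacing between readings, or a rule for assigning a reading to a nominal time.

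The same footnotes treat early PK draws more strictly: "PK sampling: pre-dose (-60 min), < 2 h (± 5 min").

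**The concern.** A tolerance as wide as the spacing does not secure a series. With ±15 min on readings 15 min apart, neighbouring readings can coincide or swap order, or drift far apart, and no deviation is recorded.

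This is the first time the product is infused in humans. Safety and tolerability is the primary objective, and the SAP lists vital signs among the primary endpoints. The protocol's summary of changes records that the 15-minute series was added on FDA advice to monitor for infusion reactions, so the spacing was deliberate. SAP section 6.4 also summarises vital signs at each time point, and values labelled 0.25 h and 0.75 h could come from the same minute after the start. First-hour timing is therefore held more tightly for PK, a secondary objective, than for infusion-reaction monitoring.

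**Working it through.** The documents state no figure to reproduce, so this is interval arithmetic on the stated times and tolerances.

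**Inputs**
- Nominal times: 15, 30, 45 and 60 min from the start of infusion (protocol 8.1 and 13.1.2; SAP Table 2).
- Tolerance: w = 15 min (footnotes to protocol Table 1 and SAP Table 2).
- Comparator: w = 5 min, the PK window before 2 h (same footnotes).

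**Formulas.** For neighbouring nominal times t1 < t2:
- window = t − w to t + w
- overlap = max(0, 2w − (t2 − t1))
- largest gap for the pair = (t2 − t1) + 2w
- smallest gap for the pair = max(0, (t2 − t1) − 2w)

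**Results**

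| | w = 15 min | w = 5 min |
|---|---|---|
| Windows (min) | 0-30, 15-45, 30-60, 45-75 | 10-20, 25-35, 40-50, 55-65 |
| Overlap of neighbours | 2×15 − 15 = 15 | 2×5 − 15 < 0, so 0 |
| Latest compliant first reading | 15 + 15 = minute 30 | 15 + 5 = minute 20 |
| Largest gap | 15 + 30 = 45 | 15 + 10 = 25 |
| Smallest gap | 0 | 15 − 10 = 5 |
| Fewest occasions that fall in all four windows | 2 | 4 |

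At ±15 min, minute 30 lies in the windows for 0.25, 0.5 and 0.75 h, and minute 45 lies in those for 0.5, 0.75 and 1 h. Two occasions, minute 30 and any minute from 45 to 75, fall in all four windows.

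**Is the 45 min gap attainable?** All whole-minute timings were enumerated with the four readings separate, in order, and the first at minute 1 or later. The largest gaps are:
- 44 min between readings 1 and 2 (minutes 1 and 45)
- 45 min between readings 2 and 3 (minutes 15 and 60)
- 45 min between readings 3 and 4 (minutes 30 and 75)

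The set 10, 15, 60, 65 is one example. It needs no reading at minute 0.

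**Smaller drift.** If two neighbouring readings are each off by k min in opposite directions, the gap is 15 + 2k:
- k = 5: 25 min
- k = 7.5: 30 min
- k = 10: 35 min
- k = 15: 45 min

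**Where the overlap stops.** The windows for 1, 1.5 and 2 h are 45-75, 75-105 and 105-135 min. They touch but do not overlap, so the overlap is confined to the first four readings.

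**The case against.** The strongest reply is that the weight is small.

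- **Observation continues between readings.** Protocol section 10.3 says "Intravenous dose administration will be conducted and monitored by CRU personnel", and section 13.2 adds "Subjects will be instructed to report AEs during the study and staff will query subjects regarding AEs throughout the study". The Investigator may repeat abnormal readings (13.1.2) and add or change collection times (SAP 6.4). A PK draw is due at 0.5 h within ±5 min, so someone is at the bedside between minutes 25 and 35, inside the 45 min gap of the example. All this stands and keeps the practical risk modest. But a PK draw is not a blood pressure or pulse reading, repeats follow an abnormal value, and extra times are permitted but not required. None of it secures the scheduled series.
- **Four separate readings are scheduled, so one cannot serve for three.** This is a fair reading of the schedule. The count of two occasions only describes how far the windows overlap. The 45 min gap does not depend on it, because it was found with the readings separate and in order.
- **Later gaps are longer.** With ±15 min kept after 1 h, minutes 55 and 105 are 50 min apart and minutes 75 and 135 are 60 min apart. This is true, but those readings are scheduled 30 min apart, come after the infusion, and have windows that do not overlap.
- **±5 min is a choice.** Any window below 7.5 min removes the overlap, and at exactly 7.5 min the windows abut. ±5 min is preferred because the site already works to it for PK draws before 2 h.
- **Nothing formal depends on it.** Safety summaries are descriptive, and stopping rests on AE grades and committee judgement. This stands too.

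**Conclusion.** The concern holds. At ±15 min each neighbouring pair of the four windows overlaps by 15 min, and a compliant series can have a gap of 45 min against the 15 min scheduled.

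This rests on the window and times as printed, counted from the start of infusion, with the 0.25 h reading taken after the start. The figures are limits of what is compliant and do not claim that staff would time readings in this way. The effect on the descriptive vital-sign summaries is small, and no effect on dose escalation is shown. The change is worth making because it is nearly free and protects safety monitoring in a first-in-human infusion.

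**What to change.** In the footnotes to protocol Table 1 and SAP Table 2, set ±5 min for the vital signs at 0.25, 0.5, 0.75 and 1 h. Keep ±15 min for later post-dose times to 12 h.

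No rule on the order of procedures is needed, because protocol section 12 already says "Other assessments e.g. ECG, vital signs etc. may be taken before or after PK sample collection".

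The cost is one line in each document. The downside is a few more recorded timing deviations, mainly at 0.5 and 1 h, where a PK draw is also due. SAP section 5 lists the post-dose draws at "0.5, 1, 1.5, 2, 4, 6, 9, 12, 24, 36, and 48 hours relative to start of infusion", so none falls at 0.25 or 0.75 h.
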